2.4 Study Hypothesis

The primary hypothesis of this study is that in addition to SoC, AB103 will demonstrate a clinically significant treatment benefit over placebo.

This hypothesis will be addressed by measuring the effect of AB103 on a composite of clinical parameters associated with the disease course of patients with NSTI, using a responder analysis. A responding patient must meet all the 5 parameters of the composite clinical success end point, while a non-responding patient can fail by not meeting any one of the parameters. These analyses are designed to demonstrate that in addition to being safe, one dose of 0.5 mg/kg of AB103 will:

Improve systemic signs of the infection by improving organ function of patients compared to placebo as measured by:

- Survival at Day 28
- mSOFA score on Day 14 and change from baseline to Day 14 ≥ 3. Day 14 mSOFA score of ≤1 and a change from baseline (pre-treatment) to Day 14 ≥3 will be required for a patient to achieve the primary composite clinical success endpoint (NICCE)

Improve the local signs of the infection, as measured by:

- Reduced number of debridements, counted to Day 14. No more than 3 debridements to Day 14 will be required for a patient to achieve composite clinical success
- No amputation after the first debridement (amputation on the first debridement is not considered a failure). A patient will be required to have had no amputations done after the first surgical procedure in order to achieve composite clinical success.

A full response will be considered as meeting **all** the above systemic and local criteria for response, in addition to being alive at Day 28.

A conditional co-primary endpoint will be evaluated only if the two-sided p-value for the primary responder analysis is ≤ 0.01 .

The conditional co-primary endpoint also involves a responder analysis that involves being alive at Day 28 and demonstrating improvement in the local signs of infection as measured by:

- A reduced number of debridements, counted to Day 14. A patient with ≤3 debridements to Day 14 will be considered a responding patient
- No amputation after the first debridement (amputation during the first debridement is not considered a failure). A patient with no amputations performed after the first surgical procedure will be considered a responding patient in relation to this parameter.

3. SELECTION OF STUDY POPULATION

To be enrolled in the study, patients must meet ALL of the inclusion criteria and NONE of the exclusion criteria.

3.1 Inclusion Criteria

- 1. Age: ≥ 12 years
- 2. Surgical confirmation of NSTI by attending surgeon (e.g. presence of necrotic tissue, thrombosed vessels in the subcutaneous tissue, lack of bleeding and "dishwater" (cloudy, thin, gray) fluid) due to presumed bacterial infection (necrotizing cellulitis (most commonly group A strep), necrotizing fasciitis, necrotizing myositis and myonecrosis, NSTI of the perineum, bacterial synergistic gangrene, Clostridial gas gangrene) that may be supported by specific signs and symptoms (e.g. tense edema outside area of compromised skin, pain disproportionate to appearance, skin discoloration, ecchymosis, blisters/bullae, necrosis, tense edema, crepitus and/or subcutaneous gas).
 - Patients with NSTI following intra-abdominal operation are eligible if adequate source control of intra-abdominal process has been established
- mSOFA score ≥3 (in any one or combination of the 5 major components of SOFA score with any one organ component having a score of at least 2: cardiovascular, respiratory, renal, coagulation, CNS), measured as close as possible to the first debridement, (but before first debridement is performed).
- 4. IV drug administration within 6 hours from the clinical diagnosis and the decision at the study site, to have an urgent surgical exploration and debridement (drug should not be administered until surgical confirmation is established).
- 5. If a woman is of childbearing potential, she must consistently use an acceptable method of contraception from baseline through Day 28. Acceptable birth control methods include oral contraceptive medication, an intrauterine device (IUD), an injectable contraceptive (such as Depo-Provera®), a birth control patch, a barrier method (such as condom or diaphragm with spermicide) or abstinence.
 - Non-childbearing potential is defined as current tubal ligation, hysterectomy, or ovariectomy or post-menopause (1 year without menses with an appropriate clinical profile at the appropriate age e.g. >45 years).
- 6. If a male patient's sexual partner is of childbearing potential, the male patient must acknowledge that they will consistently use an acceptable method of contraception (defined above) from baseline through Day 28.
- 7. Signed and dated ICF as defined by the IRB and, if applicable, California Bill of Rights. By signing the ICF, the patient agrees to release any medical records pursuant to current HIPAA Guidelines. If patient is unable to comprehend or sign the ICF, patient's legally acceptable representative may sign the ICF.

3.2 Exclusion Criteria

- 1. BMI >51;
- 2. Patient who has been operated at least once for the current NSTI infection and had a curative deep tissue debridement (patients who underwent prior diagnostic minor surgery are allowed to enter into the study);
- 3. Patients with overt peripheral vascular disease in the involved area associated with ischemic wounds/ulcers or gangrene, and /or other significant symptoms of inadequate vascular supply or where limb amputation is considered likely within 7 days due to the peripheral vascular disease;
- 4. Diabetic patients with peripheral vascular disease who present with below the ankle infection;
- 5. Patient with burn wounds;
- 6. Current condition of: (a) Inability to maintain a mean arterial pressure > 50 mmHg and/or systolic blood pressure > 70 mmHg for at least 1 hour prior to screening despite the presence of vasopressors and IV fluids or (b) a patient with respiratory failure such that an SaO₂ of 80% cannot be achieved or (c) a patient with refractory coagulopathy (INR >5) or thrombocytopenia (platelet count <20,000) that does not partially correct with administration of appropriate factors or blood products;

- 7. Chronic neurological impairment that leads to a neuro mSOFA component ≥ 2 ;
- 8. Recent cerebrovascular accident in the last 3 months;
- 9. Patients with cardiac arrest requiring cardiopulmonary resuscitation within the past 30 days;
- 10. Patient is not expected to survive throughout 28 days of study due to underlying medical condition, such as poorly controlled neoplasm (e.g. Stage III or IV cancer);
- 11. Patient or patient's family are not committed to aggressive management of the patient's condition, or the combination of necrotizing skin infection and underlying illness makes it unlikely that life support will be maintained;
- 12. Any concurrent medical condition, which in the opinion of the Investigator, may compromise the safety of the patient or the objectives of the study or the patient will not benefit from treatment such as:
 - CHF {NYHA class III-IV}
 - Severe COPD {GOLD stage III-IV. or chronic hypoxemia (PaO₂ <55 mmHg) on room air, or chronic use of home ventilation, or unable to climb stairs or perform household duties due to chronic obstructive disease resulting in severe exercise restriction, or use of continuous home oxygen prior to hospital admission (sleep apnoea treated with continuous positive airway pressure or biphasic positive airway pressure oxygen during sleep is acceptable)}
 - Liver dysfunction {Childs-Pugh class C}
 - Immunosuppression (see Appendix F, Section 15.6 for list of excluded immunosuppressive medications)
 - \circ Neutropenia < 1,000 cells/mm³ not due to the underlying infection
 - Idiopathic Thrombocytopenic Purpura

- Receiving or about to receive chemotherapy or biologic anti-cancer treatment although hormonal manipulation therapies for breast and prostate malignancies are permitted
- Hematological and lymphatic malignancies in the last 5 years
- 13. Known HIV infection with CD4 count < 200 cells/mm3 or < 14% of all lymphocytes;
- 14. Patients with known chronic kidney disease (documented pre-illness creatinine value(s) ≥2.0) or patients receiving renal replacement therapy for chronic kidney disease: either hemodialysis, peritoneal dialysis, hemofiltration such as Continuous Veno-Venous Hemofiltration (CVVH) or hemodiafiltration
- 15. Patients that are treated with continuous hemofiltration (e.g. Continuous Veno-Venous Hemofiltration) for acute kidney dysfunction, not due to NSTI, starting prior to study drug administration.

Exception: Patients with acute kidney dysfunction due to NSTI may be enrolled in the event that the patient is off the treatment from time of study drug administration and up to at least one hour post study drug administration.

- 16. Pregnant or lactating women; Women of childbearing potential must have a negative β-subunit hCG pregnancy test immediately prior to study entry.
- 17. Previous enrollment in a clinical trial involving investigational drug or a medical device within 30 days before provision of written informed consent for the study or within five half-lives of the investigational drug, whichever is longer.
- 18. Previous enrollment in this protocol, ATB-202 or the Phase 2 NSTI trial of AB103, ATB-201, or the current Phase 2 SA-AKI trial of AB103, ATB-203.

3.3 Withdrawal

Patients will be informed that they are free to withdraw from the study at any time and for any reason. The date the patient is withdrawn from the study and the reason for withdrawal will be recorded in the eCRF and in the source documentation.

3.3.1 Criteria for Premature Discontinuation from Study

In rare instances, the patient (or Investigator) may determine that he/she is not able to make all visits required by the protocol. Possible reasons for discontinuation from the study may be:

- Withdrawal of consent
- Lost to follow-up
- Other reasons such as administrative reasons

4. INVESTIGATIONAL PLAN

4.1 Study Rationale

4.1.1 Dose Selection Rationale

Selection of a dose regimen for the pivotal Phase 3 study was based on the safety results from the Phase 1 and 2 trials and efficacy results from Phase 2. Evidence for dose response in the Phase 2 study is based on consistency across multiple domains of outcome variables. In several efficacy parameters, a linear dose response emerged for individual endpoints. In addition, to adjust for group differences at baseline and for the distorted distribution of values, non-parametric comparisons between dose groups were used, which indicated that 0.5 mg/kg had an advantage over the 0.25 mg/kg, especially in cases of patients that stayed for a longer time in the ICU or required ventilation. Overall, based on the reproducibility of the dose response in the various parameters, and given that there was no change in the safety profile when increasing the dose from 0.25 mg/kg to 0.50 mg/kg, Atox Bio believes that the 0.5 mg/kg given as a single dose is the optimal dose for the proposed Phase 3 ATB-202 clinical trial.

The comparative effect of high and low dose groups is shown in Table 5.

Outcome	0.5 mg/kg	0.25 mg/kg
Total SOFA at Day 14		
Individual organ SOFA score at Day 14		
Changes in total score between days 1-14		
Percent of patients with organ failure at Day 14		
SOFA score in patients with established organ		
failure at Day 1		
Debridements to Day 7 or 28		
ICU stay		\checkmark
Ventilation days		
Hospital stay		
Inflammatory biomarkers (systemic)	\checkmark	
Inflammatory biomarkers (local infection site)	\checkmark	
Mortality	\checkmark	\checkmark

Table 5: Comparative effect of high and low dose groups - Study ATB-201

 $\sqrt{-}$ higher effect size compared to Placebo.

The determination of this dose has also been discussed with the FDA. Overall, the dose and dosing regimen for the pivotal study is based on: (i) the Phase 2 results demonstrated a strong and consistent effect of the 0.5 mg/kg; (ii) the pre-clinical data demonstrated that the 5 mg/kg dose (equivalent to human 0.5 mg/kg dose) consistently provided optimal efficacy; (iii) pre-clinical data demonstrated a bell shape dose response curve, common to many immunomodulatory and peptide therapies, in which a single dose of 5 mg/kg (mouse) is optimal, with higher doses being less efficacious.

Therefore, a single dose of 0.5 mg/kg was considered to provide the most favorable risk/benefit for this patient population with severe and potentially life-threatening necrotizing skin and skin structure infection.

4.2 Allocation of Treatment, Randomization and Study Drug Administration

4.2.1 Allocation of Treatment and Randomization

Once the patient has a clinical diagnosis of bacterial NSTI at the study site and a decision for urgent surgical wound exploration and debridement has been taken, all inclusion/exclusion criteria have to be verified and an ICF has to be obtained. The pharmacist should be notified. The pharmacist will get the treatment allocation via a webbased dedicated (Interactive Web Response, IWR) software available only to the study pharmacist. All other study-related personnel, hospital care givers, the Sponsor and the patient will remain blinded.

Following allocation of treatment and surgical confirmation of NSTI, the study pharmacist will prepare the study drug (sites may choose to have the study pharmacist prepare study drug after treatment allocation but before surgical confirmation of NSTI but study drug can only be administered upon surgical confirmation of NSTI). When the study drug is ready for infusion, last verification of inclusion/exclusion criteria will take place pertaining to the 6 hours' time limit for drug administration (and any significant change in patient condition that would warrant the patient's exclusion from the study).

4.2.2 Study Drug Administration

The drug can be administered at either one of 2 time points: Option A: during surgery and Option B: after surgery. In both instances, the study drug administration must be initiated within 6 hours of the time at which the patient was clinically diagnosed at the study site as having NSTI and the decision was made to undergo urgent surgical debridement. The NSTI diagnosis should also be confirmed surgically, and in case it is not confirmed surgically the patient will not receive the drug and will be considered as a screening failure.

In case study drug has been prepared but a patient did not receive it, the web-based dedicated software will be updated to ensure an overall 1:1 ratio between the AB103 and placebo treatment groups.

4.3 Schedule of Procedures/Visits

A schedule of study assessments is shown in Appendix A, Section 15.1 the protocol. Visiting nursing services, including Symphony Clinical Research, are allowed for outpatient visits. Symphony Clinical Research is contracted to evaluate subjects as outpatients as early as Day 10 through Month 3.

4.3.1 Visit 1: Screening

Evaluation starts once a clinical diagnosis of NSTI was entertained and a decision for urgent surgical wound exploration and debridement was made:

• Obtain ICF

- Verification of Inclusion/Exclusion criteria
- Randomization & study drug preparation (study drug should not be prepared until there is surgical confirmation of NSTI)
- Demographics, Medical history, Infected lesion history, Concomitant medications, Vital signs, Height, Weight, calculate BMI, PE
- Urine output recording to start from time of ICU admission and while Foley catheter is in place (captured in 6 hour intervals based on calendar day)
- Recording baseline signs and symptoms and AEs/SAEs (AEs of Day 0 are AEs/ SAEs starting after obtaining ICF until study drug administration)
- Safety baseline laboratory tests:
 - Full chemistry panel
 - Obtain complete blood count (CBC) with differential and platelet count (sample can be same as that required to be taken in conjunction with the RNA expression profile test sample)
- C-reactive protein (CRP)
- Arterial blood gases and FiO2 (if applicable) -may use SpO2 value if arterial blood gas is not clinically indicated
- Collect data on acute renal replacement therapy
- Collect data on plasma or platelet transfusion
- Blood culture for both aerobic and anaerobic bacteria
- Pregnancy test if applicable (blood or urine whichever is faster)
- Screening mSOFA score measurements must be performed prior to first surgery: should be evaluated any time after arrival at the hospital (may include referring hospital), although no more than 6 hours prior to anticipated first surgery. Sites are encouraged to re-evaluate mSOFA score as close to surgery as feasible for patients not meeting mSOFA ≥3 inclusion criteria during initial screening. Baseline mSOFA will include measurements of the score components in the following organ/systems (with any one organ having a score of at least 2 at screening): respiratory, cardiovascular, renal, coagulation and CNS
- APACHE II score, LRINEC and Anaya scores (measurement for these scores will be collected and scores will be calculated retrospectively). The clinical parameters of these scores (respiratory, cardiovascular, vital signs) should be taken as close as possible to the surgery, but prior to the surgical anesthesia or any other surgical related procedures e.g. mechanical ventilation. The worst laboratory values available within 24 hours of surgical intervention for NSTI should be recorded. Critical care parameters (dates and times of assisted ventilation, vasopressor use, ICU and hospital admission and discharge)
- Local lesion assessment and evidence of amputation (excision to a joint space)
- Surgery for NSTI and confirmation of diagnosis. Record time of surgery
- During surgery: Tissue samples for microbiology
- 12 Lead ECG (can be performed any time during screening period or just prior to study drug administration)

- Upon study drug administration patient is transited to visit 2 (either during or after the surgery)
- Collect blood for serum for storage (immunogenicity testing)
- Collect urine and blood for plasma for storage (AKI biomarker analysis)
- Collect whole blood for leukocyte transcriptome (RNA expression) profiling
- Perform randomization

4.3.2 Visit 2 (Day 1)

Starts ONLY upon study drug administration and terminates at the end of the calendar day. Study drug may be given either during surgery or immediately after the surgery.

- Drug administration should be completed within 6 hours from the clinical diagnosis of NSTI and a decision at the study site for urgent surgical wound exploration and debridement
- Collect data on operative procedures(see Section 6.2.6.1 for description of adjudication of operative procedures for assignment of study defined debridement)
- Collect data on acute renal replacement therapy
- Collect data on plasma or platelet transfusion
- Collection of AEs/ SAEs
- Concomitant medications
- Vital signs (first set of vitals on that day)
- Symptom-driven interim PE
- 12-Lead ECG at the end of study drug infusion, at 4-6 hours and 12-24 hours post administration of study drug
- Urine output (should be recorded continuously from time of ICU admission to Day 7, if still in ICU and Foley catheter in place, using 6 hour intervals and by calendar day)
- Weight, only if not collected at screening
- Collect data on additional amputations
- Critical care parameters (dates and times of assisted ventilation, vasopressor use, ICU /hospital stay)
- Systemic response: mSOFA score. Measurements will be collected within 16-24 hours post study drug administration, unless the patient is scheduled to undergo additional debridement; in such case data collection for mSOFA parameters will be taken prior to the next debridement
 - All efforts should be made to obtain the actual measurements of SOFA parameters at these visits-may use SpO2 value (and record FiO2) if arterial blood gas is not clinically indicated
 - Obtain serum creatinine
 - Obtain CBC with differential and platelet count (sample can be same as that required to be taken in conjunction with the RNA expression profile test sample)
- Assess lesion status (healing/progression/significant change in appearance) if accessible for visible assessment at time of debridement or routine dressing change

- Collect whole blood for leukocyte transcriptome (RNA expression) profiling at 4-6 hours post study drug dose
- Survival

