4.3.3 Visit 3 (Day 2)

- Collect data on operative procedures
- Urine output (should be recorded continuously from time of ICU admission to Day 7, if still in ICU and Foley catheter in place, using 6 hour intervals and by calendar day)
- Collection of AEs/ SAEs
- Collect data on additional amputations
- Collect data on acute renal replacement therapy
- Collect data on plasma or platelet transfusion
- Concomitant medications
- Vital signs (to be taken during the morning tests)
- Critical care parameters (dates and times of assisted ventilation, vasopressor use, ICU /hospital stay)
- Systemic response: mSOFA score (measurements will be collected and scores will be calculated retrospectively).
 - All efforts should be made to obtain the actual measurements of SOFA parameters at these visits-may use SpO2 value if arterial blood gas is not clinically indicated
 - Obtain serum creatinine
 - Obtain CBC with differential and platelet count (sample can be same as that required to be taken in conjunction with the RNA expression profile test sample but must be on the same calendar day as study Day 2)
- Assess lesion status (healing/progression/significant change in appearance) if accessible for visible assessment at time of debridement or routine dressing change
- Collect urine and blood for plasma for storage (AKI biomarker analysis) at 24±4 hours after study drug administration
- Collect whole blood for leukocyte transcriptome (RNA expression) profiling at 24±4 hours after study drug administration
 - CBC with differential required to be obtained in conjunction with sample for RNA expression profile best
- Record Survival

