^q Tissue for microbiology will be taken at the 1st debridement (performed at visit 1), to be used for identification of pathogen(s), susceptibility to antimicrobial drugs and Gram stain. Obtain tissue for microbiological culture if debridement performed on Day 3 (Visit 4). If culture from debridement on Day 3 is positive, then repeat culture if subsequent debridement(s) performed.

^r Adverse events including SAEs will be collected from obtaining ICF through day 28; AEs that are not resolved should be followed-up until resolution or until determined as stable and due to known cause.

^s AEs of day 0 are baseline AEs (not TEAE) starting after obtaining ICF until study drug administration.

^t Assess lesion status (healing/progression/significant change in appearance) if accessible for visible assessment at time of debridement or routine dressing change

Visit	1	2	3	4	5	6	7	8	9	10
	Screening	Day 1	Day 2	Day 3	Day 7 ±1 day	Day 10 ±1 day	Day 14 ±1 days	Day 21 ±1 days	Day 29 +2 days	3 months ±5 days
Collect data on acute renal replacement therapy, plasma and/or platelet transfusion									•	
Evaluation of adequacy of antimicrobial treatment				Х						
Critical care and hospital stay parameters ^u										
mSOFA score ^v	Х	X ^w	Х	Х	Х	Х	Х	Х	Х	
APACHE II score ^x	X									
LRINEC and Anaya ^y scores	Х									
Survival										
Hospital readmissions ^z									Х	Х
Serum for immunogenicity ^{aa}	X						Х		Х	X

^u Hospital length of stay (days), ICU stay (days), ICU free days, Mechanical ventilation days/mechanical ventilation free days;

^v Screening mSOFA: To be calculated prospectively from time patient presents at the hospital (may include referring hospital) but within 6 hours prior to first debridement. Screening mSOFA may be reassessed up to actual time of surgery if initial mSOFA evaluation had score <3. To include measurements of 5 organ systems to achieve score of \geq 3, in any one or more organs, with any one organ having a score of at least 2: cardiovascular, respiratory, renal, coagulation and CNS (To include evaluation of oxygenation either directly by arterial blood gas test or by calculation of PaO₂ from SpO₂, in case it is not possible to obtain arterial blood to determine the SOFA respiratory parameter), ^w Subsequent mSOFA data collection (Days 1, 2, 3, 7, 10, 14, 21 and 29): taken once a day, in the morning (between 6AM until 12 noon) adjusted to the time of normal

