routine assessment activities. However, if surgery is performed during the usual time of the assessments, these assessments should then be collected at a minimum of 2 hours post-surgery. The following blood samples must be taken: platelets, and creatinine. In addition, clinical parameters should be taken (see Section 15.5). For SpO2 \leq 95%, check for the most consistent result and record that value.

^x For the required laboratory and clinical parameters (see Section 15.5)

^y For the required laboratory and clinical parameters (see Section 15.1).

² Capture data on any readmissions within 30 days of original hospital discharge

^{aa} 6 mL blood for serum for storage (for immunogenicity testing) at Screening, Days 14 and 29, and Month 3

Final Protocol ATB-202 version 4.0 23 Aug 2018

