8.6 Distribution of mSOFA scores Over Time

Table 14.2.2.1 summarizes mSOFA and its 5 components over time, from screening to Day 28. Since bilirubin is collected only at screening and at Day 7 and 14, observed SOFA total scores will also be summarized at these three timepoints.

Table 14.2.2.2 provides the same summary after application of last-value-carried forward (LOCF) to Day 14. LOCF was not applied after patient death or for missing Day 21 or Day 28 mSOFA.

Table 14.2.2.3 summarizes changes from Day 0 in mSOFA and in each of its components to Days 1, 2, 3, 7, 10, 14, 21, and 28 without applying LOCF.

Table 14.2.2.4 provides the same summary after application of LOCF to Day 14. This table only summarizes mSOFA to Day 14 because there was no LOCF imputation for missing mSOFA after Day 14 and so the results for Days 21 and 28 are identical to the table summarizing mSOFA without LOCF.

Tables 14.2.2.5 and 14.2.2.6 provides the same summaries for observed and LOCF imputed mSOFA and components to Days 28 and 14, respectively, but for changes from Day 1 rather than Day 0.

The data displayed in Tables 14.2.2.1 to 14.2.2.6 will be graphically displayed in line plots comparing between treatment groups using line plot (Figures 5 to 10) and box and whiskers plots (Figures 11 to 14).

Table 14.2.2.7 will summarize mSOFA and organ specific values at screening, 16 - 24 hours post dose, and changes from screening to 16 - 24 hours post dose.

Table 14.2.2.8 will summarize mSOFA without the Glasgow Coma Score and without the Glasgow Coma Score Among Patients on Ventilation and Medications Affecting GCS to Day 28.

8.7 Time to resolution of mSOFA score to ≤ 1

Life tables for time to resolution of mSOFA score ≤ 1 will be provided in Tables 14.2.3.1 and 14.2.3.2 for the 0.50 mg/kg and placebo treated groups, respectively, to Day 14. Comparative Kaplan-Meier survival curves will be provided in Figure 15.

For these analyses, patients who die prior to Day 14 will be considered censored at one day past Day 14 and assumed to have never achieved mSOFA \leq 1. Log rank statistic will be used to assess if the distributions of times to symptom resolution differ between treatment groups.

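### Two conflicting timing rules leave the Day 1 mSOFA undefined, and in late-dosed patients the Day 1 score can be measured after the Day 2 score

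*Protocol*

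**What the plan says.** Of Day 1, Protocol 4.3.2 says that it "Starts ONLY upon study drug administration and terminates at the end of the calendar day". The following statements then set the time of the Day 1 mSOFA.

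- **Protocol 4.3.2:** "Measurements will be collected within 16-24 hours post study drug administration", followed by an exception: "unless the patient is scheduled to undergo additional debridement; in such case data collection for mSOFA parameters will be taken prior to the next debridement". Table 6 (Protocol 6.2.14) repeats the 16-24 h draw under Visit 2, Day 1.
- **Protocol Appendix A, footnote w:** the marker sits on the Day 1 mSOFA cell, and the note lists Days 1, 2, 3, 7, 10, 14, 21 and 29. The data are "taken once a day, in the morning (between 6AM until 12 noon) adjusted to the time of normal" routine assessments. It has its own exception: "if surgery is performed during the usual time of the assessments, these assessments should then be collected at a minimum of 2 hours" after that surgery.

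Day 2 is handled as a calendar day. Protocol 4.3.3 requires that the Day 2 blood count "must be on the same calendar day as study Day 2".

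The SAP draws on both rules. Section 3.5.4 defers to the time and events schedule, which leads to footnote w, while section 8.6 plans a table of scores at 16-24 h post dose (Table 14.2.2.7). The Day 1 score is a covariate in the MMRM for mSOFA (5.8). It is the reference for Tables 14.2.2.5 and 14.2.2.6, which repeat the summaries "but for changes from Day 1 rather than Day 0". It is also available to last observation carried forward (LOCF; 5.2 and 5.10.1). Neither document says which timing rule governs Day 1, or that scores are ordered by actual time.

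**The concern.** A score labelled Day 1 should have one definition and should come before the score labelled Day 2. Here a site could follow either rule and be within the protocol, and the two rules can give times that differ by most of a day. The exceptions also point in opposite directions: Protocol 4.3.2 places the score before the next debridement, whereas footnote w moves it to after a surgery that occupies the morning.

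Three uses of the score are exposed:

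- **MMRM covariate.** SAP 5.8 includes the Day 1 score to capture the patient's state after the first operation. If it is measured after the Day 2 outcome, the model adjusts an outcome for something observed later. If it is measured on the morning before an afternoon dose, it may not reflect the postoperative state at all.
- **Change from Day 1.** When the clock order is reversed, the Day 1 to Day 2 change has the wrong sign.
- **LOCF among the first visits.** Taken by visit label, the last score may be the older of the two.

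**Working it through.** The plan states no figure on this point, so there is none to reproduce. The check is clock arithmetic.

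**Inputs**
- Dosing hour t, in hours from midnight at the start of Day 1. The documents give no distribution of dosing times.
- Day 1 ends at hour 24 (Protocol 4.3.2), so calendar Day 2 is hours 24 to 48.
- 16-24 h rule: window [t+16, t+24] (Protocol 4.3.2 and Table 6).
- Footnote w: Day 1 morning is [6, 12] and Day 2 morning is [30, 36] (Appendix A).
- Patients with only one debridement in Phase 2: 20%, 26% and 33% by arm (Protocol 1.1.3.3.2, Table 3), so 67-80% had more than one.

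**Step 1: where the 16-24 h window falls**
- Wholly on Day 2: t+16 ≥ 24, so t ≥ 8 (dose from 08:00).
- Wholly after the Day 2 morning window: t+16 ≥ 36, so t ≥ 20 (dose from 20:00).
- Possibly after the Day 2 score: t+24 > 30, so t > 6.

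**Step 2: where footnote w puts the score**
The Day 1 morning closes at hour 12. For t > 12 it closes before dosing, although Day 1 begins only at dosing. The footnote's own exception helps only if surgery took that morning slot.

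**Step 3: chance that the Day 1 score follows the Day 2 score**
This assumes patients bound by the 16-24 h rule, with sampling uniform within each window. For a dose at 12:00 the Day 1 window is [28, 36]. Six of its eight hours overlap [30, 36], and within the overlap either order is equally likely, so the chance is 6/8 × 1/2 = 38%.

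| Dose at | Chance |
|---|---|
| 06:00 or earlier | 0% |
| 08:00 | 4% |
| 12:00 | 38% |
| 14:00 | 63% |
| 16:00 | 83% |
| 18:00 | 96% |
| 20:00 or later | 100% |

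**Step 4: shares of patients, ignoring the re-debridement exception**
With doses spread evenly over 24 h, the share wholly on Day 2 is (24 − 8)/24 = 66.7%, and the share wholly after the Day 2 morning is (24 − 20)/24 = 16.7%. The table adds other assumed spreads.

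| Assumed dosing times | Wholly on Day 2 | Wholly after Day 2 morning | Expected reversal |
|---|---|---|---|
| 00:00-24:00 | 67% | 17% | 46% |
| 00:00-08:00 | 0% | 0% | 0.3% |
| 08:00-20:00 | 100% | 0% | 58% |
| 12:00-24:00 | 100% | 33% | 85% |

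**Step 5: allowing for the exception**
Suppose every patient with more than one debridement is exempt, exemption is unrelated to dosing hour, and dosing is spread evenly. Then 20-33% of patients remain bound.
- Bound and certain to fall on Day 2: 0.20 × 2/3 = 13% to 0.33 × 2/3 = 22% of all patients.
- Bound and certain to follow the Day 2 morning window: 0.20 × 1/6 = 3.3% to 0.33 × 1/6 = 5.5%.

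Given the even spread, 13-22% is a lower bound for scores landing on Day 2, because an exempt patient's score may also be taken that day.

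**The case against.** The best defence is that Protocol 4.3.2 is the Day 1-specific rule, is repeated in Table 6, and has a matching table in the SAP, so a sensible site would follow it. Footnote w is also softer than a fixed window, since it bends to routine activity and to surgery. Both points are fair, but neither removes the conflict. Footnote w names Day 1 and is attached to the Day 1 cell, no text ranks the two rules, and the 16-24 h rule still overruns the midnight end of Day 1 for practically every dose.

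The defence is stronger against wider readings that a reader might be tempted to draw:

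- **That most patients have a Day 1 score on Day 2.** This is not shown. Dosing times are unknown, and the re-debridement exception could cover most patients.
- **That visit-ordered analyses run backwards.** Only the Day 1 to Day 2 step can reverse. Day 3 and later keep their order.
- **That time to resolution is distorted.** SAP 5.2.3 counts it from drug administration, so it need not reverse if actual times are used.
- **That one blood sample serves both days.** The windows can overlap, but Table 6 lists separate Day 1 and Day 2 draws.

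**Conclusion.** The conflict is real but its reach is limited. For patients bound by the 16-24 h rule, a dose from 08:00 puts the Day 1 score on calendar Day 2, and a dose after 20:00 puts it after the Day 2 morning window. These two statements follow from the protocol's clock times alone. The population shares do not: 67% and 17% rest on evenly spread dosing and ignore the exception. The 13-22% figure rests on evenly spread dosing and on full exemption of every patient with more than one debridement.

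The consequence is an inconsistently timed Day 1 score in supportive analyses, namely the MMRM covariate, change from Day 1, and LOCF among the first visits. It would be wrong to infer a threat to the study's success criterion. NICCE uses the screening and Day 14 scores (SAP 5.2.2), so it is reached only if Day 14 is carried forward from Day 1 or 2, which requires Days 3, 7 and 10 to be missing as well. The conditional co-primary endpoint contains no mSOFA component.

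**What to change.** 1. Reconcile Protocol 4.3.2, Table 6 and Appendix A footnote w so that a single rule defines the Day 1 mSOFA and fits the definition of Day 1, including when re-debridement is scheduled. Which rule to keep is for the sponsor to decide.
2. Record the date and time of each early mSOFA assessment. The documents do not show that these times are captured.
3. State in SAP 5.2 and 5.8 that early mSOFA values are ordered by actual time from study drug administration for LOCF, change from Day 1 and the MMRM.

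The cost is a protocol clarification, a short SAP addition, and capture of assessment times if they are not already recorded. No extra assessments are needed.
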